5.3 Lifestyle restrictions

5.3.1 Meals and dietary restrictions

No meal or dietary restrictions are required during this study.

5.3.2 Caffeine, alcohol, and tobacco

No caffeine, alcohol, and tobacco restrictions are required during this study; any restrictions (for the purposes of routine clinical management) are left to the judgment of the Investigator.

5.3.3 Activity

No activity restrictions are required during this study.

5.4 Screen failures

Screen failures are defined as participants who consent to participate in the clinical study but are not subsequently entered in the study. A minimal set of screen failure information is required to ensure transparent reporting of screen failure participants to meet the Consolidated Standards of Reporting Trials (CONSORT) publishing requirements and to respond to queries from regulatory authorities. Minimal information includes demography, screen failure details, eligibility criteria, and any SAE.

Individuals who do not meet the criteria for participation in this study (screen failure) may be rescreened.

Tests that result in ALT, AST, or ALP up to 25% above the exclusion limit may be repeated only once for confirmation. This one-time repeat testing may be within the initial screening window or as part of a rescreening following a screen failure. Upon retesting, study participants whose results remain outside the exclusion limit are not to be enrolled.

6 STUDY TREATMENTS

Study treatment is defined as any investigational treatment(s), marketed product(s), placebo, or medical device(s) intended to be administered to a study participant according to the study protocol.

6.1 Treatments administered

Certolizumab pegol is an engineered, humanized, monoclonal antibody Fab' fragment with specificity for human TNF α , produced in an *Escherichia coli* expression system. The antibody fragment is subsequently purified and conjugated with high molecular weight PEG (40kDa).

Intervention name	CZP
Type	Biologic
Dose formulation	Pre-filled syringe (1mL)
Unit dose strength(s)	200mg/mL
Dosage levels	400mg loading dose for first 3 doses (at Weeks 0, 2, and 4), followed by 200mg Q2W maintenance dose thereafter
Route of administration	sc injection
Use	Experimental
Sourcing	Provided by UCB Clinical Trial Supply or designee
Packaging and labeling	The study medication is packaged according to GMP guidelines and applicable laws or regulations; study medication is labeled in accordance with current ICH, GCP, and GMP and includes any locally required statements.
Current/Former names	CDP870, Cimzia, CZP

CZP=certolizumab pegol; GCP=Good Clinical Practice; GMP=Good Manufacturing Practice; ICH=International Council for Harmonisation; Q2W=every 2 weeks; sc=subcutaneous

6.2 Preparation, handling, storage, and accountability requirements

The Investigator or designee must confirm appropriate temperature conditions have been maintained during transit for all study treatment received and any discrepancies reported and resolved before use of the study treatment.

Only participants enrolled in the study may receive study treatment and only authorized site staff and home health nurses may supply and administer study treatment prior to Week 12. After Week 12, study participants will have the choice to self-administer CZP or receive treatment at the clinic/study site. All study treatments must be stored in a secure, environmentally-controlled, and monitored (manual or automated) area in accordance with the labeled storage conditions with access limited to the Investigator and authorized site staff.

The Investigator, institution, or the head of the medical institution (where applicable) is responsible for study treatment accountability, reconciliation, and record maintenance (ie, receipt, reconciliation, and final disposition records).

In case an out-of-range temperature is noted, it must be immediately reported as per instructions contained in the IMP Handling Manual.

The Investigator (or designee) will instruct the participant to store the study medication following the instructions on the label.

Further guidance and information for the final disposition of unused study treatment are provided in the Study Reference Manual.

6.2.1 Drug accountability

The Case Report Form (CRF) will be used to record study medication dispensing and return information on a by-participant basis and will serve as source documentation during the course of the study. Details of any study medication lost, damaged (due to breakage or wastage), not used, partially used, disposed of at the study site, or returned to the Sponsor or designee must also be recorded on the appropriate forms. All supplies and pharmacy documentation must be made available throughout the study for UCB (or designee) to review.

The Investigator (or designee) is responsible for retaining all used, unused, and partially used containers of study medication until returned or destroyed.

The Investigator may assign some of the Investigator's duties for drug accountability at the study site to an appropriate pharmacist/designee.

The Investigator must ensure that the study medication is used only in accordance with this protocol.

Periodically, and/or after completion of the clinical phase of the study, all used (including empty containers)/partially used, unused, damaged, and/or expired study medication must be reconciled and either destroyed at the site according to local laws, regulations, and UCB Standard Operating Procedures or returned to UCB (or designee). Investigational medicinal product intended for the study cannot be used for any other purpose than that described in this protocol.

6.3 Measures to minimize bias: randomization and blinding

This is an open-label study.

6.4 Treatment compliance

At each visit after study medication is dispensed, participants must return all unused study medication and empty study medication containers. Drug accountability must be done in the participant's presence in order to obtain explanations regarding discrepancies in compliance with the dosing regimen. Drug accountability must be recorded on the Drug Accountability Form.

6.5 Concomitant medication(s)/treatment(s)

6.5.1 Permitted concomitant treatments (medications and therapies)

The following concomitant medications are permitted during the study:

- Methotrexate, under the following conditions:
 - Participant must have been stable for at least 1 month before Screening.
 - The participant's route of MTX administration and dose of MTX should not change until after Week 12 of the study.
 - The (minimum of) 8 participants who are not taking MTX upon study entry cannot begin MTX until after Week 12 of the Treatment Period.
 - Dose reductions are permitted at any point during the study for safety reasons.

Other medications not explicitly prohibited per Section 6.5.2 are also included as permitted concomitant treatments.

6.5.2 Prohibited concomitant treatments (medications and therapies)

The following concomitant medications are prohibited during the study:

- Conventional synthetic DMARDs (csDMARDs) other than MTX (see Section 6.5.1 for MTX parameters).
- Targeted synthetic DMARDs (tsDMARDs), eg, the Janus kinase inhibitor, tofacitinib.
- Biologic DMARDs (CZP study medication excepted).
- Any experimental (biological or nonbiological) therapy (within or outside a clinical study).
- Live and live attenuated vaccinations including, but not limited to, oral polio, chicken pox (varicella), measles-mumps-rubella, nasal influenza, and rotavirus. No data are available on the response to live vaccinations or the secondary transmission of infection by live vaccines in study participants receiving CZP.

6.5.3 Rescue medication

The Sponsor will not supply rescue medications. Such medicines should be sourced/prescribed locally by the treating physician. The following rescue medications may be used:

- Any RA rescue medications available, excluding biologic DMARDs (CZP study medication excepted), csDMARDs other than MTX (see Section 6.5.1), and tsDMARDs. Any participants who use a biologic DMARD (other than study medication), csDMARD other than MTX (as per Section 6.5.1), or tsDMARD should be immediately withdrawn from the study.

The date and time of rescue medication administration as well as the name and dosage regimen of the rescue medication must be recorded.

If the study participant requires administration of a biologic DMARD, csDMARD other than MTX (as per Section 6.5.1), or tsDMARD, they must be removed from the study (Section 7.2).

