4.4 End of study definition

A participant is considered to have completed the study if he/she has completed all portions (Screening, Baseline Visit, Treatment Period [through Week 24], and SFU) of the study.

Following investigational medicinal product (IMP) administration at Week 24, participants may transition to treatment with commercial CZP in consultation with their health care professional. The SFU Visit will be conducted 70 days post last administration of IMP.

The end of the study is defined as the date of the last visit of the last participant in the study.

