6.8 Treatment after the end of the study

Study participants may transition to treatment with commercially-available CZP in consultation with their health care professional following completion of the last administration of IMP.

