7.2 Participant Discontinuation/Withdrawal from the study

Participants are free to withdraw from the study at any time, without prejudice to their continued care.

A participant may withdraw from the study at any time at his/her own request, or may be withdrawn at any time at the discretion of the Investigator for safety, behavioral, compliance, or administrative reasons.

If the participant withdraws consent for disclosure of future information, the Sponsor may retain and continue to use any data collected before such a withdrawal of consent.

If a participant withdraws from the study, he/she may request destruction of any samples taken and not tested, and the Investigator must document this in the site study records.

See the Schedule of Activities (Section 1.3) for data to be collected at the time of study discontinuation and follow-up and for any further evaluations that need to be completed.

Participants should be withdrawn from the study if any of the following events occur:

1. Participant develops an illness that would interfere with his/her continued participation.
2. Participant is noncompliant with the study procedures or medications in the opinion of the Investigator.
3. Participant takes prohibited concomitant medications as defined in this protocol.
4. Participant may withdrawal at any time due to lack of efficacy. At study discontinuation, the participant may be offered other treatment options, at the Investigator's discretion.
5. Participant withdraws his/her consent.
6. Participant has confirmation of a pregnancy during the study, as evidenced by a positive pregnancy test.
7. The Sponsor or a regulatory agency requests withdrawal of the participant.

Investigators should contact the Medical Monitor, whenever possible, to discuss the withdrawal of a participant in advance.

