#### **5.4.1.2.2 Treatment-emergent SAEs**

A treatment-emergent adverse event (TEAE) is defined as events that have a start date on or following the first administration of study treatment in RA0138 through the final administration of study treatment+70 days through SFU visit. The treatment-emergent serious adverse event (TESAE) will follow the same definition and also mark serious adverse event as “Yes” in the adverse events CRF form.

The analysis for secondary endpoint for treatment-emergent SAEs will be included as follows:

- Incidence of treatment-emergent SAEs
- Incidence of treatment-emergent SAEs by Maximum Intensity
- Incidence of treatment-emergent SAEs by Maximum Relationship

Serious AEs summaries will be ordered by alphabetical SOC, HLT and decreasing frequency of PT within SOC in the CZP column for tables including event counts.

A listing will be presented for SS for treatment-emergent SAEs. This will include the SOC, HLT and PT, onset date/time and outcome date/time of the event (including relative days), the AE duration, pattern of event, serious/intensity, relationship, action taken and outcome. In addition, the listing will flag hospitalization, SAEs, and AE of special interest.

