#### Incidence and prevalence:

- Total prevalence of pre-Ab overall and by treatment group. Total prevalence of pre-Ab:  $n/NN$  % number of participants that have a pre-ADA positive ADA sample status, with NN being the denominator defined as all participants having an evaluable baseline ADA sample.
- Overall ADA incidence and by treatment group. Treatment-Emergent Anti-CZP Antibody Positivity Activity for combined results of treatment-boosted ADA-positive participants and treatment induced ADA-positive participants.  $n/N$  % of participants that are treatment emergent, with N being the denominator defined as all participants except the participants categorized as inconclusive.
- Summary tables of the time point of the first occurrence of treatment emergent (TE) ADA positivity (i.e first ADA sampling time point with ADA positive status if participant is pre-ADA negative or first ADA sampling time point with fold difference increase from Baseline > the MSR if participant is pre-ADA positive) for study participants in category 2 and 5. The table will summarize the number and percentage of TE ADA positive participants who present first occurrence of TE ADA positivity at the specified time point and will include the cumulative number and cumulative percentage of participants at each time point. In case of ADA samples with missing or inconclusive status before the first ADA sampling time point considered TE ADA positive, the time point of the first occurrence of TE ADA positivity will be reported as  $\leq$  than the respective ADA time point. In case of pre-ADA present in more than 10% of the study participants, the table is split out between ADA participant category 2 and 5. The denominator for % calculations will be the total number of TE ADA positive participants.
- Number and percentage of study participant Baseline Anti-CZP status and Treatment-Emergent Anti-CZP Antibody Status will be summarized during the entire study. The change in category from Baseline ADA status including ADA-, ADA+, Missing and total will be presented in

shift tables at each post-Baseline treatment treatment-emergent anti-CZP antibody status. Treatment Treatment-Emergent Anti-CZP Antibody Status will be categorized as below:

- Negative : Treatment Treatment-Emergent Anti-CZP Antibody Status is ADAb-
  - Positive <512 : Treatment Treatment-Emergent Anti-CZP Antibody Status is ADAb+ and ADAb titer is less than 512.

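### Protocol 4.4 and 6.8 permit commercial CZP after the last study dose while 6.5.2, 6.5.3 and 7.2 prohibit it on their wording; SFU timing conflicts between protocol and SAP, and SFU ADA and late safety data pool participants on and off CZP

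*Protocol*

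**What the plan says.** **Permission.** Protocol 4.4 says that after the Week 24 dose "participants may transition to treatment with commercial CZP in consultation with their health care professional". Protocol 6.8 repeats it: "Study participants may transition to treatment with commercially-available CZP in consultation with their health care professional". Section 4.4 counts a participant as finished only after having "completed all portions (Screening, Baseline Visit, Treatment Period [through Week 24], and SFU) of the study", and places the SFU 70 days after the last dose of investigational product. The Schedule of Activities gives that visit a ±7 day window.

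**Prohibition.** Protocol 6.5.2 lists treatments prohibited during the study, among them "Biologic DMARDs (CZP study medication excepted"; study CZP is the only exception. Protocol 6.5.3 requires immediate withdrawal, in a rule that begins "Any participants who use a biologic DMARD (other than study medication". Protocol 7.2 includes among its withdrawal events: "Participant takes prohibited concomitant medications as defined in this protocol". Under Protocol 6.1, study CZP comes from the sponsor's clinical trial supply, so a commercial supply is not study medication.

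**SAP.** Section 5.1.1.1.3 keeps the 70-day SFU but sets it at 30 days for participants continuing on the commercial product. Section 5.2 defines a completer by Visit 16 at 70 days. The treatment-emergent adverse event (TEAE) window in 5.4.1.2.2 runs "through the final administration of study treatment+70 days through SFU visit", and time at risk in 5.6.1 adds 70 days to the last dose. Section 5.5.1.1.2 tabulates ADA status by visit, participant category, incidence and time of "first occurrence of treatment emergent (TE) ADA positivity". None of these is split by commercial CZP use, and subgroup analyses (5.8) are marked not applicable.

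**The concern.** The 70 days between the last study dose and the SFU fall under both rules. A site reading 4.4 and 6.8 keeps a participant who moves to commercial CZP. A site reading 6.5.2, 6.5.3 and 7.2 literally withdraws the same participant. Sites could therefore handle identical participants differently, and disposition would reflect which section was read.

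If transitioners are kept, two things are at stake. First, their SFU could fall at 30 or at 70 days depending on which document is followed, while the safety windows assume 70 for everyone. Second, the SFU summaries mix participants about 10 weeks off drug with participants still being dosed. Circulating drug can mask antibodies, so an SFU ADA result does not mean the same thing in the two groups. The SFU sample feeds the overall ADA category, incidence and first-occurrence tables as well as its own by-visit row. Events that begin after commercial doses enter the TEAE tables without being marked as such.

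**Working it through.** **1. The stated study duration.** Inputs: screening 28 days, treatment 168 days, SFU 70 days (Protocol 1.1 and 1.3).

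- 28 + 168 + 70 = 266 days; 266 / 7 = 38.0 weeks. This reproduces the stated duration of about 38 weeks.
- With the SAP's 30-day follow-up: 28 + 168 + 30 = 226 days; 226 / 7 = 32.3 weeks.

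**2. SFU window.** 70 ± 7 gives days 63 to 77 after the last dose. Day 30 lies outside it, so a transitioner seen at 30 days as SAP 5.1.1.1.3 says is off the protocol schedule and does not match SAP 5.2.

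**3. Safety windows.** For a participant dosed through Week 24, time at risk under SAP 5.6.1 is 168 + 70 = 238 days.

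- Observed to a 30-day visit: 168 + 30 = 198 days; 198 / 238 = 83%.
- Remainder: 70 − 30 = 40 days.

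Protocol 8.3.1 collects adverse events only until the SFU, but asks for serious events for up to 70 days after each participant's end of study. The 40-day gap is therefore mainly one of non-serious events.

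**4. Exposure at the SFU.** The commercial schedule is not given. Assume dosing simply continues every 14 days from the last study dose.

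- 70-day SFU: doses on days 14, 28, 42 and 56, with a fifth due on day 70, so 4 to 5.
- 30-day SFU: doses on days 14 and 28, so 2.

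Under either timing, a transitioner is on CZP at the visit.

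**5. How many.** The transition rate is not given. Over an assumed range of 25% to 75% of 30 participants, about 8 to 22 would be on CZP at the SFU and 22 to 8 off it. With 25 participants, the split runs from 6 on and 19 off to 19 on and 6 off.

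**6. ADA.** Post-baseline samples are scheduled at Weeks 6, 12, 24 and the SFU, so the SFU is 1 of 4. SAP 5.5.1.1.2 calls a non-positive sample inconclusive when the corresponding drug level exceeds the assay's drug tolerance. The Schedule of Activities has a CZP concentration at Weeks 6, 12 and 24 but none at V16, although SAP 5.4.1 lists concentrations through Visit 16. From scheduled data the rule cannot be applied at the SFU, and a drug-masked negative in a transitioner could not be identified as inconclusive.

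**7. Whether existing definitions identify transitioners.** SAP 6.1.5.2 requires a concomitant medication to start before last dose + 14 days. A first commercial dose exactly on day 14 fails, because 14 < 14 is false. The SAP's concomitant class would miss the participants in question, although the Schedule of Activities reviews medications at V16.

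**The case against.** The strongest reply is that no real conflict exists. Sections 4.4 and 6.8 are specific permissions, 6.8 is headed as treatment after the end of the study, 6.5.2 deals with concomitant treatment and 6.5.3 with rescue. A specific permission normally governs a general prohibition. That stands as a reading of intent: withdrawing transitioners is probably not what the sponsor means. It does not settle the wording. Completion in 4.4 includes the SFU, the prohibition has no end date, and no passage exempts commercial CZP.

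Five stronger readings are tempting, and the documents do not support them.

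- *That the SAP ignores transitioners.* It gives them a 30-day follow-up. That does not remove the pooling, and it adds a timing conflict.
- *That withdrawal would lose the SFU sample and visit.* V16 is a combined SFU and early discontinuation column with ADA, laboratory tests and vital signs, Protocol 7.2 points to that schedule, and SAP 5.1.1.1.4 generally maps such visits to the next scheduled one. The timing would change; the data need not be lost.
- *That transitioners would count as important protocol deviations.* The criteria sit in a separate document that is not available here.
- *That on-drug SFU samples would be classed inconclusive.* Without a scheduled concentration at V16, the problem runs the other way: masked negatives would stand as negatives.
- *That no result through the SFU could be interpreted.* ADA is shown by visit, the ADA listing gives days since study medication, and event listings give onset dates and relative days. The TEAE definition is a time window; relationship to CZP is reported separately.

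It is also fair that this is a single-arm descriptive study and that ADA is outside the primary and secondary endpoints.

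**Conclusion.** The point holds as a conflict of rules with a limited analysis consequence. Protocol 4.4 and 6.8 cannot be applied together with 6.5.2, 6.5.3 and 7.2 as worded. The 30-day follow-up in SAP 5.1.1.1.3 cannot be squared with the protocol's 70 ±7 days, with SAP 5.2, or with safety windows that extend 40 days past a 30-day visit. One of four post-baseline ADA time points and the safety data after Week 24 combine participants on and off CZP, with nothing in the summaries to separate them.

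The dose counts assume uninterrupted every-2-week continuation. The number affected depends on a transition rate the documents do not give; with few transitioners the effect would be small. The primary Cmin and AUC, taken between Weeks 10 and 12, and the ADA results at Weeks 6, 12 and 24 are untouched. Severity is minor to moderate.

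**What to change.** Reconcile Protocol 4.4, 6.5.2, 6.5.3, 6.8 and 7.2 with SAP 5.1.1.1.3 and 5.2, so that one statement covers commercial CZP between the last study dose and the SFU, and one SFU timing applies. Which rule and which timing should stand is for the sponsor.

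In the SAP:

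- Derive a flag from the recorded start date of commercial CZP, not from the concomitant-medication definition, which excludes starts on or after last dose + 14 days.
- Show SFU ADA status and titre separately for participants with and without commercial CZP since the last study dose, with a footnote that no concentration is scheduled at V16 to apply the drug-tolerance rule.
- Flag TEAEs that start after the first commercial dose.
- Align the TEAE and time-at-risk windows with the follow-up actually observed.

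The cost is a protocol clarification, one derived variable, and a few split rows and footnotes in tables already planned. The start date should be available from the medication review at V16, so no new assessment is needed. The drawback is smaller cells at the SFU.
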